2.4 Schema

Cohort 1

W = Week

Cohort 2

The 110 participants in Cohort 1 and 90 participants in Cohort 2 were randomized to one of the two study arms with an active GSK 744 to placebo ratio of 3:1, stratified by gender and region (US and non US), as follows:

Cohort 1

Arm 1: 82 participants received daily oral 744 (30 mg tablets) for 4 weeks, followed by an one week washout period, to establish safety and tolerability, followed by intra-muscular (IM) gluteal injections of 800 mg of 744LA (administered as two sequential 400 mg gluteal injections) at three time points at 12 week intervals as: Week 5, Week 17, and Week 29.

Arm 2: 28 participants received daily oral matching placebo and IM injections of vehicle-matched placebo on the same schedule as Arm 1.

Cohort 2

Arm 1: Approximately 66 participants will receive daily oral 744 (30 mg tablets) for 4 weeks, followed by a one week washout period, to establish safety and tolerability, followed by intra-muscular (IM) gluteal injections of 600 mg of 744LA (administered as one 600 mg gluteal injection) at five time points at 4 and 8 week intervals as: Week 5, Week 9, Week 17, Week 25, and Week 33.

Arm 2: Approximately 22 participants will receive daily oral matching placebo and IM injections of vehicle-matched placebo on the same schedule as Arm 1.

All participants will receive HIV testing with pre- and post-test counseling, in addition to risk-reduction counseling and condoms and lubricant. All participants will be followed according to the Schedule of Evaluations and Procedures provided in HPTN077 protocol Appendices I-IV.

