3 OBJECTIVES AND ENDPOINTS

3.1 Primary Objectives and Endpoints

Primary Objective

- Evaluate the safety and tolerability of the injectable agent, GSK1265744 long acting (744LA) injectable (800 mg dose administered at three time points at 12 week intervals) through Week 41 in HIV-uninfected men and women
- Evaluate the safety and tolerability of the injectable agent GSK1265744 long acting (744LA) injectable (600 mg dose administered at two time points at 4 week intervals, followed by three time points at 8 week intervals), through Week 41 in HIV-uninfected men and women.

Primary Endpoints

Safety endpoint: Proportion of participants experiencing any Grade 2 or higher clinical AEs and laboratory abnormalities that occur from the initial injection to 12 weeks after the last injection among participants who receive at least one injection (injectable phase only)

Tolerability endpoint: Proportion of participants who receive at least 1 injection and who discontinue receiving injections prior to the full course of 3 injections due to intolerance of injection (including but not limited to ISR), frequency of injections, burden of study procedures, or any AE.

These cohorts may be aggregated for an overall analysis if appropriate.

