9.6 Tolerability

To assess tolerability of 744 LA, the proportion (with 95% CI) of subjects who terminate from receiving injections prior to the full course due to AEs, intolerance of injection, frequency of injections, or burden of procedures related to injections out of those subjects that received at least one injection by cohort and treatment arm will be provided. The proportion will be compared between the treatment arms by cohort and in aggregate using Fisher Exact test.

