11.2 Safety and Tolerability Analysis

11.2.1 Lists of Tables

Table 8 Permanent discontinuation of study regimen by treatment arm (a) during the oral phase, (b) during the injection phase, and (c) during the on-treatment

Table 9 Adverse experiences by MedDRA preferred term and severity (ordered by system organ class) (a) during the oral phase, (b) during the injection phase, (c) during the tail phase, and (d) during the on-treatment

Table 10 Adverse experiences by MedDRA preferred term and severity – including severe, potential life-threatening or fatal events only (a) during the oral phase, (b) during the injection phase, (c) during the tail phase, and (d) during the on-treatment

Table 11 Adverse experiences by MedDRA preferred term and relationship to study product (a) during the oral phase, (b) during the injection phase, (c) during the tail phase, and (d) during the on-treatment

Table 12 Elevation of liver chemistry and other lab test events (a) during the oral phase, (b) during the injection phase, (c) during the tail phase, and (d) during the on-treatment

Table 13 Summary of Injection Site Reaction Characteristics

Table 14 Summary of characteristics of common ISR symptoms

Table 15 Summary of change in laboratory test at follow up from baseline by visit and cohort

Table 16 Summary of ECG values by treatment arm and visit

Table 17 Summary of maximum change in corrected QTc intervals by category for change from baseline

Table 18 Listing of expedited adverse events (EAE) or serious adverse events (SAE) with the details of the events including severity, relationship to study product, time between onset and last injection, number of injections received (if the events occurring after the 1st injection), and a summary of the event

Table 19 Proportion of participants experiencing any Grade 2 or higher clinical AEs and laboratory abnormalities that occur (a) during the oral phase, (b) during the injection phase (c) during the tail phase, and (d) during the on-treatment period

Table 20 The proportion of participants who discontinue the study product for reasons of toxicity, tolerability, or acceptability (a) prior to completion of the full oral phase and (b) prior to completion of the full injection phase.

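### Sections 3.1 and 9.6 give different scope to one of the four stopping reasons in the primary tolerability endpoint: burden from any study procedure, or only from procedures tied to injections

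*SAP*

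**What the plan says.** Section 3.1 lists tolerability under Primary Endpoints: "Tolerability endpoint: Proportion of participants who receive at least 1 injection and who discontinue receiving injections prior to the full course of 3 injections", for any of four reasons, namely "intolerance of injection (including but not limited to ISR), frequency of injections, burden of study procedures, or any AE".

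Section 9.6 specifies the analysis. It counts those who end injections before the full course "due to AEs, intolerance of injection, frequency of injections, or burden of procedures related to injections". The denominator is the same as in 3.1: "out of those subjects that received at least one injection by cohort and treatment arm will be provided". The test follows: "The proportion will be compared between the treatment arms by cohort and in aggregate using Fisher Exact test".

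Three other places touch on discontinuation:
- Section 9.5.6 tabulates treatment discontinuation by reason and arm, for the oral and injection phases separately.
- Section 11.2.1, Table 20, reports "The proportion of participants who discontinue the study product for reasons of toxicity, tolerability, or acceptability". That follows the secondary endpoint in Section 3.2.
- The Appendix derives study populations, BMI and the phase of an AE. It has no derivation for the tolerability event.

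**The concern.** The SAP states the event definition of a primary endpoint twice, with different content. A programmer working from 9.6 would code a narrower numerator than the one 3.1 promises, and a reader of the report who knows only 3.1 would not see the difference.

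The conflict also reaches a secondary endpoint. For women using injectable hormonal contraception, Section 3.2 points back to the endpoint as defined earlier in Section 3, while Section 9.12 points back to the analyses described earlier in Section 9. Those two routes lead to the two different lists.

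Timing adds some weight. Section 10.2.1 puts permanent discontinuation by arm, and a listing of reasons, into the closed monitoring report. Section 5.2 lets the primary study team see unblinded summary tables at the interim analysis. Section 1 allows the SAP to be updated up to the final analysis. A list left open now could be settled after such information exists.

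**Working it through.** **Step 1. The reasons side by side.**

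| Reason | Section 3.1 | Section 9.6 | Same? |
|---|---|---|---|
| Adverse events | any AE | AEs | yes, in substance |
| Intolerance of injection | yes, with a note that it is not limited to ISR | yes, without the note | yes, in substance |
| Frequency of injections | yes | yes | yes |
| Burden of procedures | study procedures, unrestricted | only those related to injections | no, 9.6 is narrower |

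The injection-related set lies inside the unrestricted set. For the burden category, every event under 9.6 is an event under 3.1, but not the reverse. With the same denominator and the same handling of the full course, the 9.6 proportion can equal the 3.1 proportion or fall below it, and never exceed it.

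**Step 2. Search for a rule that settles it.** Section 9.5.6 displays reasons but does not say which are events. Table 20 uses a third wording that belongs to the secondary endpoint. The Appendix has no mapping of discontinuation reasons. No rule of precedence appears.

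**Step 3. Scale.** The SAP states no expected rate, power or count for this endpoint, so there is no figure to reproduce. The shift per reclassified participant is 1/n. The arm sizes come from Section 2.4 (for example "Arm 1: 82 participants received daily oral 744 (30 mg tablets) for 4 weeks"). They count everyone in the arm, while the denominator is limited to those injected at least once. They are therefore upper bounds on n, and 1/n is a lower bound on the shift.

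| Group | n | Shift per participant |
|---|---|---|
| Cohort 1 active | 82 | 1/82 = 1.2 points |
| Cohort 1 placebo | 28 | 1/28 = 3.6 points |
| Cohort 2 active | about 66 | 1/66 = 1.5 points |
| Cohort 2 placebo | about 22 | 1/22 = 4.5 points |
| Aggregate active | 82 + 66 = 148 | 1/148 = 0.7 points |
| Aggregate placebo | 28 + 22 = 50 | 1/50 = 2.0 points |

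The Cohort 2 sizes are approximate: 66 + 22 = 88, while the same section gives 90 for the cohort. Splitting 90 at 3:1 gives 67.5 and 22.5, and shifts of 1.5 and 4.4 points, so this makes little difference.

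**Step 4. Illustration with assumed counts (not from the SAP).** Take 4 undisputed events among 82 in Cohort 1 active, and 1 among 28 on placebo. The intervals use the Wilson method that 9.5.5 names for the safety proportions; 9.6 asks for a 95% CI without naming a method.

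| Added general-burden stops, active | Proportion | Wilson 95% CI | Fisher p against 1/28 |
|---|---|---|---|
| 0 | 4/82 = 4.9% | 1.9 to 11.9 | 1.0 |
| 1 | 5/82 = 6.1% | 2.6 to 13.5 | 1.0 |
| 3 | 7/82 = 8.5% | 4.2 to 16.6 | 0.68 |
| 5 | 9/82 = 11.0% | 5.9 to 19.6 | 0.45 |

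On these counts the estimate and interval move visibly, but the Fisher comparison stays far from significance.

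**The case against.** The strongest reply is that the gap is narrow. Section 4.4 labels the visits between injections as safety visits following a given injection. Section 3.2 ties PK sampling to time points after each injection. Sections 9.8 to 9.10 place the questionnaires at injection visits or, for the satisfaction and acceptability forms, one week after. Much of the injection-phase workload can fairly be called injection-related, and the SAP defines neither phrase. This stands. A reader might infer that anyone who stops because of visits or blood draws is a non-event under 9.6, but the documents do not support so firm a classification. The conflict is certain only for stops due solely to procedures unrelated to injections.

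The tabulation of reasons in 9.5.6 is a partial safeguard. It lets a reader see burden stops by arm, as finely as reasons are recorded. It limits hidden reclassification but does not fix the primary numerator.

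Three further inferences go too far:
- That the two lists differ throughout. Only one category differs.
- That the narrower list lowers the proportion in both arms and changes the Fisher result. That needs such stops to occur, in both arms for the first part, and in sufficient number for the second. No count is given, and it could be zero.
- That the list will be chosen with knowledge of the arms. The plan does not prevent this, but nothing in it suggests an intention to do so.

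It can also be said that 3.1 is not plainly the more reliable text, since its sentence speaks of a full course of three injections although Cohort 2 has five (Section 2.3). That is a separate inconsistency, and those passages need reconciling too. It is a reason to check 3.1, not a reason to leave the two lists in conflict.

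**Conclusion.** The point holds for the burden category only. As written, 9.6 can yield a smaller primary numerator than 3.1 from the same recorded reasons, and the SAP offers no way to decide between them.

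The likely effect is modest. Each affected participant matters more on placebo than on active because the placebo arms are small, but how many are affected is unknown. The per-participant figures assume that everyone in the arm was injected, so they are minimum shifts, subject to the approximate Cohort 2 sizes. The illustrative intervals rest on assumed counts and say nothing about what the trial will find. No figure stated in the SAP depends on the choice.

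It should still be corrected, because the endpoint is primary and the correction is almost free.

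**What to change.** 1. Use one identical reason list in 3.1 and 9.6. By default, carry the unrestricted burden category of 3.1 into 9.6, so that the analysis estimates the stated primary endpoint. If the narrowing was deliberate, amend 3.1 instead and give the reason.
2. Before unblinding, add to the Appendix a mapping of each recorded stop reason to event or non-event.
3. Refer to that single definition in 9.12, so that the contraceptive-subset endpoint follows it.
4. Optionally, if the CRF reasons separate general from injection-related burden, show the injection-related subset as a supportive row. The SAP does not show the codes, so this cannot be assumed.

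The cost is one phrase in 9.6, a short mapping table and at most one extra table row. No new data are needed. The reported proportion may come out slightly higher than under the present 9.6 wording.

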3.2 Secondary Objectives and Endpoints

Secondary Objectives

- Evaluate the safety and tolerability of GSK1265744 (daily oral 744 + 744LA) for 76 weeks of follow-up after final injection (each cohort will be analyzed separately)
- Evaluate the safety and tolerability of oral 744 from Week 0 to Week 5

- Evaluate the pharmacokinetics of 744LA administered as 800 mg IM every 12 weeks for 52 weeks of follow-up after final injection
- Evaluate differential pharmacokinetics of 744LA in participants by age, gender, race, ethnicity, weight, body mass index (BMI), and smoking status
- Evaluate the acceptability of 744LA injections
- Evaluate the effect of 744LA on sexual risk behavior by change from enrollment for repeat assessments to during the study period
- Evaluate HIV incidence and antiretroviral drug resistance, if any participants acquire HIV infection during the study
- Evaluate the safety, tolerability and pharmacokinetics of 744LA in the subset of women who use a hormone-based contraceptive

Secondary Endpoints

- Proportion of participants who discontinue either oral or injectable study product for reasons of toxicity, tolerability, or acceptability prior to completion of the full oral and injectable phases
- Proportion of participants experiencing Grade 2 or higher clinical AEs and laboratory abnormalities during 52 weeks following final injection (safety) and any AE that leads to discontinuation (tolerability) during the aggregate oral and injectable phases
- Proportion of participants experiencing Grade 2 or higher clinical AEs and laboratory abnormalities (safety) and any AE that leads to discontinuation (tolerability) in the oral phase and washout period
- Plasma drug levels of GSK1265744 at designated time points after each injection of 744LA (by cohort only)
- Plasma drug levels of GSK1265744 at designated time points after each injection of 744LA stratified by age, gender, race, ethnicity, weight, BMI, and smoking status
- Proportion of participants willing to use an injectable agent such as the study product for HIV prevention in the future
- Change from enrolment of self-reported sexual behaviour (number of sexual partners, episodes of unprotected anal and/or vaginal intercourse) during the study period using a standardized assessment tool (in aggregate only)
- Number of incident HIV infections through the study period, including number with treatment emergent resistance
- Proportion of injectable hormonal-contraception-using female participants who reach a safety or tolerability endpoint as defined above

3.3 Exploratory Objectives and Endpoints

Exploratory Objectives

- Explore relationships between safety parameters and GSK1265744 concentrations and/or participant demographic factors
- Explore genetic factors that may impact the pharmacokinetics of 744LA
- Perform secondary laboratory assessments which may include evaluation of factors related to HIV infection, hepatitis infection, or sexually transmitted infections (STIs); antiretroviral (ARV) drug use; pharmacogenomics; characterization of HIV in infected participants; and evaluation of laboratory assays related to the study objectives

Exploratory Endpoints

- Relationships between observed AEs and pharmacokinetic parameters (including but not limited to GSK1265744 C_{max} and C_{min} and AUC) and participant demographic data (individual and in aggregate)
- Relationships between pharmacogenetics (evaluated by Genome Wide Association Study [GWAS], which will inform subsequent targeted analyses) and pharmacokinetic parameters or incidence of AEs (any and by organ class and individual AE)

4 STUDY DESIGN

4.1 Participants

200 men and women at low to minimal risk for acquiring HIV infection, ages 18 to 65, randomized 3:1, with approximately 150 in the active drug arm, and 50 in the placebo arm. It is anticipated that approximately 60% of the enrolled participants will be women.

4.2 Design

This is a multi-site, double-blind, two-arm, randomized, placebo-controlled trial of the safety, tolerability, and acceptability of 744LA.

4.3 Study Duration

Approximately 3 years. Accrual will require approximately 16 to 24 weeks (4 – 6 months) for each cohort. Study participants in both cohorts will receive oral tablets for 4 weeks, followed by a 1 week wash out period. Cohort 1 will then receive intra-muscular injections at 3 time points over 24 weeks (6 months); cohort 2 will receive intra-muscular injections at five time points over 28 weeks (7 months). Participants in the active study product arm will be followed for 76 weeks (18 months) after their last injection. Participants in the placebo arm will be followed until 76 weeks after their last injection or until the last participant in the active study product arm in cohort 2 completes their Week 41 visit, whichever comes first, at which time the study will be unblinded to assess the primary endpoint. When all procedures related to unblinding are completed, participants in the placebo arm will no longer be followed.

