4.8 Blinding

Study site staff, with the exception of the site Pharmacist of Record or their designee, and participants will be blinded to the random assignments. Blinding will be maintained until the last participant enrolled in to the active drug arm in cohort 2 has completed their Week 41 visit (the time point of the primary endpoint of the study), and when all data related to the Week 41 visit has been entered into the database, as well as cleaned and verified. At a specified time directed by the HPTN SDMC, participants will be unblinded to their treatment assignment, and participants in the placebo arm will no longer need to be followed. Participants in the active study product arm will continued to be followed for 52 weeks after their last injection.

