5.2 Interim Analysis

An interim analysis will be performed when 50% of the participants have completed their primary endpoint visit (Week 41). All data available at that time will be included in the analysis. Pharmacokinetic data will be analyzed when approximately 50% of Cohort 1 reaches Week 29 (two troughs) for Cohort 1 participants, and when approximately 50% of Cohort 2 reaches Week 17 (two troughs) for Cohort 2.

With the approval from HPTN SMC, the unblinded summaries of the safety and pharmacokinetic data from the analysis may also be provided to the key members of the protocol team and possibly to regulatory agencies to facilitate an initiation of a phase III trial. All members of the protocol team, including GSK and ViiV Healthcare, as well as study participants will remain blinded to individual participant treatment assignment. The data from this analysis may also be combined with the interim data from a similar study being conducted by GSK/ViiV, if needed and appropriate. Pooled summaries will also be provided to the study team to share with regulators.

To maintain the integrity of the clinical study, only the following staff may be unblinded at these SMC interim analyses, as deemed necessary by the SMC: selected clinical

pharmacometrist, programmer, and statisticians who will use unblinded 744 concentrations to build the population PK models, and staff who will incorporate safety data from this analysis into regulatory documents for other studies of 744. The primary study team (medical monitor, clinical study team leader, operational scientist, data manager) should remain blinded until all subjects complete the week 41 visit and the data has been entered and cleaned and all major protocol violators have been identified. The primary study team will only receive unblinded summary tables and figures for the planned interim analysis.

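### SAP 4.3 and 4.8 end the blind and placebo follow-up when the last active Cohort 2 participant reaches Week 41, while 5.2 waits for all subjects; one trigger covering both arms is needed (minor)

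*SAP*

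**What the plan says.** The SAP describes the end of the blind in three places.

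- **4.3 Study Duration** gives placebo participants two possible ends of follow-up: 76 weeks after their own last injection, or "until the last participant in the active study product arm in cohort 2 completes their Week 41 visit, whichever comes first". Of the second event it says "at which time the study will be unblinded to assess the primary endpoint". It then adds: "When all procedures related to unblinding are completed, participants in the placebo arm will no longer be followed".
- **4.8 Blinding**, which concerns site staff and participants, states: "Blinding will be maintained until the last participant enrolled in to the active drug arm in cohort 2 has completed their Week 41 visit". It adds a second condition, "when all data related to the Week 41 visit has been entered into the database, as well as cleaned and verified", and leaves the date of unblinding to the HPTN SDMC.
- **5.2 Interim Analysis** says that the primary study team "should remain blinded until all subjects complete the week 41 visit and the data has been entered and cleaned".

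Week 41 is the primary endpoint visit in 4.4. The last Cohort 2 injection is at Week 33, and 9.5.5 closes the Cohort 2 safety window 8 weeks later, at Week 41.

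**The concern.** The trigger in 4.3 and 4.8 guarantees a complete, blinded primary window for the active arm only. A Cohort 2 placebo participant who enrolled after the last active one, or whose Week 41 visit runs late, may not have reached that visit when the trigger fires. Under 4.3 the study is unblinded at that moment.

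Two things could follow, and both would fall on placebo alone. The participant's last adverse event reports and gradings could be made with the assignment known. If the unblinding procedures finish quickly, the last days of follow-up could also be lost. Section 9.5.5 compares the proportion with a Grade 2 or higher event between arms by Fisher's exact test. Lost placebo events would lower the placebo proportion and make active treatment look relatively worse.

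**Working it through.** **1. Which clause applies.** In Cohort 2, 76 weeks after the last injection is 33 + 76 = Week 109, the final visit in 4.4. That is long after Week 41, so the active-arm event is the one that matters for the primary window.

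**2. The three rules side by side.**

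| | 4.3 | 4.8 | 5.2 |
|---|---|---|---|
| Whose Week 41 | last active, Cohort 2 | last active, Cohort 2 | all subjects |
| Data condition | none | entered, cleaned, verified; does not say whose data | entered and cleaned |
| Who is covered | the study, without limit | site staff and participants | primary study team |

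The triggers differ. No sentence in 4.3 or 4.8 expressly requires placebo Week 41 visits to be complete.

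**3. Arm sizes.** Section 2.4 gives 90 participants in Cohort 2, about 66 active and 22 placebo. At 3:1, 90 × 0.75 = 67.5 and 90 × 0.25 = 22.5, which agrees with the stated approximate figures.

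**4. Chance by enrolment order.** Assume random order.

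- Each participant is equally likely to be last, so P(last is placebo) = 22/(66 + 22) = 22/88 = 0.25.
- Each placebo participant follows all 66 active ones with probability 1/67, so the expected number is 22/67 = 0.33.
- Splits that add up to 90 give 22/90 = 0.24 and 22/69 = 0.32 (68 and 22), or 23/90 = 0.26 and 23/68 = 0.34 (67 and 23).

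A simulation of 90 participants in four strata gives 0.24 to 0.26 and 0.31 to 0.34. It takes the 16 to 24 weeks of accrual from 4.3. Uniform accrual, blocks of 4 or 8, a 60/40 gender and 50/50 region split, and visits on time or up to one week early or late are assumptions.

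**5. Length of the shortfall.** In runs where it occurs, the longest gap between the trigger and a placebo Week 41 visit is:

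| | Median | 95th percentile |
|---|---|---|
| Visits on time | 1.0 to 1.7 days | 4.5 to 7.0 days |
| Visits up to 1 week early or late | 2.5 to 3.2 days | 7.9 to 10.0 days |

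**6. Effect on the safety proportion.** The window from Week 5 to Week 41 is 36 × 7 = 252 days. Under a constant hazard, the probability that a first event falls in the last d of T days is at most (d/T)(1 − d/T)^((T − d)/d), whatever the hazard.

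- d = 3: (3/252)(249/252)^83 = 0.0044.
- d = 10: (10/252)(242/252)^24.2 = 0.015.

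Multiplied by 0.33 participants, this is about 0.0015 to 0.005 expected lost events. Divided by 22, it is about 0.007 to 0.02 percentage points of the Cohort 2 placebo arm, with no credit for any cleaning delay.

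**7. Tolerability.** This endpoint (3.1, 9.6) is stopping injections before the full course. The last Cohort 2 injection is at Week 33, which is 8 × 7 = 56 days before Week 41. A gap of up to about 10 days cannot reach back to it.

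**The case against.** The strongest reply is the second condition in 4.8. It is not limited to one arm, and its natural reading covers every participant's Week 41 data. On that reading no placebo participant can be unblinded early. Even if it covers only active participants, entry, cleaning and verification would probably take longer than a gap of days. Section 4.3 also stops placebo follow-up only once the unblinding procedures are complete, not at the trigger itself. And 5.2 speaks of the primary study team, while 4.8 speaks of sites and participants, so those two rules cover different people.

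Most of this stands, and it keeps the point small. It does not remove it. Section 4.3 lacks the data condition and unblinds the study without saying for whom, so it conflicts with 5.2 directly. Section 4.8 does not say whether its data clause covers placebo participants who have not yet had the visit. If it covers everyone, naming the active arm serves no purpose.

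The 25% is also a figure from before enrolment. Section 2.4 says "The 110 participants in Cohort 1 and 90 participants in Cohort 2 were randomized", so the SDMC may already know the actual order and could settle that part by looking.

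A reader might infer that applying an arm-specific trigger needs someone to act improperly on unblinded assignments. The SAP does not support that: the SDMC generates and maintains the randomisation (4.7), supplies the unblinded closed reports (5.1) and directs the unblinding (4.8).

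**Conclusion.** The point holds as a minor inconsistency. Sections 4.3 and 4.8 use an active-arm trigger, 5.2 uses all subjects, and 4.3 read literally permits unblinding of a Cohort 2 placebo participant shortly before the primary endpoint visit. The chance of at least one such participant by enrolment order is about 25% (expected number 0.33), and the shortfall is probably days. The risk is one-sided and bears on the safety comparison and the blind.

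Two stronger readings are tempting but unsupported.

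- One might count each affected participant as 1/22 = 4.5 percentage points of the placebo arm. Only the last days of a 252-day window are at stake, and 8.1.1 keeps all data collected before withdrawal.
- One might extend the concern to both primary endpoints. Tolerability is essentially settled by the Week 33 injection.

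The size rests on random enrolment order, roughly uniform accrual, visits within about a week of target, and a Cohort 2 window that closes at Week 41 as in 9.5.5. Much later visits, which 4.5 allows after consultation, are not quantified. Section 3.1 ends the window 12 weeks after the last injection without a cohort exception, which would be Week 45 in Cohort 2. On that reading the same simulation leaves about 4 to 6 placebo participants inside the window at the trigger in practically every run. That is a separate inconsistency, to be settled on its own, and is not counted here. The possible effect of open-label assessment on reporting is not quantified either.

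**What to change.** Write one trigger and use it in 4.3, 4.8 and 5.2: unblinding, and release of placebo participants, occur only after the last Cohort 2 participant in either arm has completed, or passed the allowable window for, the Week 41 visit, and the Week 41 data of all participants in both arms are entered, cleaned and verified. Remove the references to the active arm from the trigger in 4.3 and 4.8, and carry the data condition into 4.3.

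The cost is a wording change in three sections. In the roughly 25% of cases where enrolment order matters, the wait is about 1 to 3 days at the median and 5 to 10 days at the 95th percentile, under the assumptions above. The data-cleaning step may cover it in any case.
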